## 2.8.2 Deaths

Separate summaries will be provided for deaths, including flags for on-treatment or post-treatment follow-up.

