1.1 Background

Chronic heart failure (CHF) is a major public health problem characterized by significant mortality, frequent hospitalization, and poor quality of life, with an overall prevalence that is increasing throughout the world (Hunt SA, 2009; McMurray JJ, 2012).

Although most patients improve symptomatically during the first 24 hours with current medical treatment (Follath F, 2011), their prognosis remains poor with over 15% to 20% mortality and 30% to 40% readmission rate in the first year after discharge (Maggioni AP, 2013a). Compared with ambulatory outpatients with heart failure, those hospitalized for AHF have >10-fold increase in the risk of dying, and although this risk decreases exponentially after discharge, it remains twofold to fourfold higher 12 to 18 months later (Gheorghiade M, 2005; Lassus JP, 2013). These outcomes have not changed in the last decade, making AHF one of the most severe clinical conditions leading to hospitalization.

Despite the changes in treatment during the last decades, where ACE inhibitor therapy reduces mortality in patients with HFrEF and has been the standard of care in this disease since the 1990s following publications of trials like CONSENSUS in 1987, and SOLV-D in 1991, although ARBs may be substituted if ACE inhibitors are poorly tolerated. Beta-blockers and aldosterone antagonists have further improved survival, but mortality remains high.

LCZ696 exhibits the novel mechanism of action of an Angiotensin Receptor Neprilysin Inhibitor (ARNI) by simultaneously inhibiting neprilysin (neutral endopeptidase; NEP) via LBQ657, the active metabolite of the prodrug sacubitril, and by blocking the angiotensin II type-1 (AT₁) receptor via valsartan.

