The date when such patient starts LCZ696 treatment will represents Visit 103 and all assessment related to that visit must also be completed. All subsequent visit dates will be derived from the date of Visit 103 (i.e., visit 104 = Visit 103 + 2 weeks).

If a patient is Randomized but not treated with LCZ696 within the windows provided:

- For the **Pre-discharge** group within 7 days after Randomization;
- For the Post-discharge group either
 - a. within 2 weeks after discharge
- b. or, if due to prolonged hospital stay, between 12 and 21 days after Randomization the patient should be withdrawn.

For more details on study treatment, please refer to Section 5, and refer to the Assessment Schedule for the visit frequency during the study.

To identify early in the course of the study any potential safety or tolerability issues, two interim safety analyses will be carried out by an internal independent DMC when 30% and 60% of the patients have completed the visit at 10-weeks after Randomization (Visit 199) to assess if the study should be terminated early.

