Data from vital signs including body weight will be summarized as appropriate, , using both descriptive summary statistics, and various threshold flags; incidences of notable values will be presented in the tables and notable values will be flagged in the listings.

The following ECG variables will be summarized as appropriate, using both descriptive summary statistics and qualitative changes will be described.

Safety analyses will be performed based on the safety population. There will be no formal statistical inference analysis.

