## 2.2 Analysis sets

The following populations will be used for the statistical analyses:

- Screened set (SCR) – All patients who signed the informed consent. The SCR includes only unique screened patients.
- Randomized Population (RAN) will consist of all patients randomized.
- The full analysis set (FAS) will consist of all randomized patients with the exception of those patients who have inadvertently been randomized into the study. In addition, patients not starting treatment within protocol specified windows will be excluded from FAS. Following the intent-to-treat principle, patients will be analyzed according to the treatment to which they were assigned at randomization.
- The Safety Population (SAF) will consist of all randomized patients who received at least one dose of study drug with the exception of those patients who have inadvertently been randomized into the study. Patients will be analyzed according to treatment actually received. The safety population will be used for the analyses of safety variables.

The protocol deviation codes leading to exclusion from the analysis sets defined above are presented in the section 4.5 Rule of exclusion criteria of analysis sets.

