### 2.8.1 Adverse events (AEs)

The incidence of treatment emergent adverse events (events occurred between the first dose and the last dose of study medication, including those occurred on the first dose date or last dose date of study medication) will be summarized by primary system organ class and preferred term. Additional summaries will be provided by severity and relationship to study medication. As the analysis of treatment emergent AEs will most likely lead to a higher frequency in the pre-discharge group, due to the longer exposure duration as well as the early exposure in a well-monitored hospital setting, an additional analysis of AEs since randomization will be carried out in the FAS population; for this analysis, AEs are defined as events occurred between the randomization date and the last dose of study medication that were absent pre-randomization, or events present prior to randomization but increased in severity after randomization.

Adverse events occurring after the last dose of study medication will be summarized by primary system organ class and preferred term.

Adverse events will be reported by primary system organ class and preferred term and separately by SMQ according to the Medical Dictionary for Regulatory Activities (MedDRA).

The MedDRA version used for reporting the study will be described in a footnote.

If a subject reported more than one adverse event with the same preferred term, the adverse event with the greatest severity will be presented. If a subject reported more than one adverse event within the same primary system organ class, the subject will be counted only once with the greatest severity at the system organ class level, where applicable.

The number and percentage of subjects reporting any adverse event and adverse events adjusted for exposure during the double-blind period of the study will be summarized by primary system organ class, preferred term and treatment and also by SMQ and treatment. The most common adverse events reported ( 1 % in any group for each preferred term in the SOC-PT table or 1% in any group for each SMQ table) will be presented in descending frequency according to its incidence in <treatment group xxx > starting from the most common event.

Separate summaries will be provided for study medication related adverse events, death, serious adverse event, other significant adverse events leading to discontinuation and adverse events leading to dose adjustment.

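### By default the death summary covers only dosed patients, and because first dosing comes later in the Post-discharge arm, it is expected to omit more early deaths there and make Pre-discharge initiation look somewhat worse

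*SAP*

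**What the plan says.** - **Deaths.** SAP 2.8.2 says "Separate summaries will be provided for deaths, including flags for on-treatment or post-treatment follow-up". It gives no analysis set, no starting time and no category before the first dose.
- **Default set.** Protocol 9.5.2, which lists the incidence of death among its summaries, says "Safety analyses will be performed based on the safety population". SAP 2.2 agrees: "The safety population will be used for the analyses of safety variables". That set is "all randomized patients who received at least one dose of study drug with the exception of those patients who have inadvertently been randomized", analysed by treatment received. SAP 5.5 excludes randomised but untreated patients from it (deviation TRT04).
- **First dose.** Under protocol 3.1, Pre-discharge patients start in hospital within 7 days of randomisation. Post-discharge patients start 1 to 14 days after discharge, or on days 12 to 21 after randomisation if still in hospital on day 10. A further rule opens "If a patient is Randomized but not treated with LCZ696 within the windows provided" and ends in withdrawal of the patient.
- **Adverse events.** SAP 2.8.1 recognises that exposure is unequal and adds an FAS analysis from randomisation, in which "AEs are defined as events occurred between the randomization date and the last dose of study medication". The visible text adds nothing similar for deaths.
- **Background risk.** Protocol 1.1 gives mortality of over 15 to 20% in the first year after discharge and says of the risk of dying: "although this risk decreases exponentially after discharge".

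**The concern.** The trial compares two times of starting the same drug. A death while waiting for the first dose is an outcome of the strategy that includes the wait. A summary limited to dosed patients requires each patient to survive to the first dose, and that requirement lasts longer in the Post-discharge arm. Even if the arms have identical mortality, the table therefore leaves out more Post-discharge deaths. The same holds for SAEs, fatal or not, in patients who are never dosed.

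Protocol 3.1 states that the data are meant to inform safety and tolerability of the two starting times. Only a few deaths are expected by week 10, so losing about three from one arm could be read as a signal against early initiation.

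**Working it through.** **The plan's own figure.** The documents give no figure for deaths. Their only precision statement is for the primary risk ratio at 80% in both arms, N = 1000. SE(log RR) = √(2 × 0.20/(500 × 0.80)) = 0.0316, and exp(±1.96 × 0.0316) gives 0.94 to 1.06, as printed. This confirms 500 per arm.

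**Pre-dose period**
- Post-discharge, from the rules: the protocol summary puts randomisation at least 48 h before planned discharge, so the earliest first dose is day 2 + 1 = 3. The latest is about day 10 + 14 = 24, or days 12 to 21 by the in-hospital route.
- Pre-discharge, from the rules: days 0 to 7.
- Assumption: discharge is uniform over days 2 to 7 (mean 4.5).
- Post-discharge dosing uniform over 1 to 14 days after discharge: mean 4.5 + 7.5 = day 12.
- Pre-discharge dosing uniform from randomisation to 12 h before discharge: mean (4.5 − 0.5)/2 = day 2.
- Average difference: 12 − 2 = 10 days.

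**Deaths left out, constant hazard, equal true mortality.** Hazard h = −ln(1 − m)/365.25 for one-year mortality m. Expected deaths by day t = 500 × (1 − exp(−ht)). Apparent ratio = (total − Pre lost)/(total − Post lost).

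| | m = 15% | m = 20% |
|---|---|---|
| Post deaths before first dose (t = 12) | 2.66 | 3.65 |
| Pre deaths before first dose (t = 2) | 0.44 | 0.61 |
| Total per arm, week 10 (t = 70) | 15.33 | 20.93 |
| Pre/Post ratio, week 10 | 14.89/12.67 = 1.18 | 20.32/17.28 = 1.18 |
| Total per arm, week 26 (t = 182) | 38.89 | 52.62 |
| Pre/Post ratio, week 26 | 38.45/36.23 = 1.06 | 52.01/48.97 = 1.06 |

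About 17% of Post-discharge deaths by week 10 are lost (2.66/15.33), against 3% of Pre-discharge deaths (0.44/15.33). Discharge over days 2 to 4 or 2 to 10 instead gives 15 to 20% of Post-discharge deaths lost. Across these assumptions the ratio is about 1.16 to 1.19 at week 10 and 1.05 to 1.07 at week 26. The last digit depends on whether randomised or dosed patients form the denominator.

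**Falling hazard.** Protocol 1.1 puts the risk at more than 10-fold that of outpatients, falling to two- to fourfold at 12 to 18 months. Taking 10 as the start, an exponential fall that matches these multiples gives about 1.18 to 1.20 at week 10 and 1.07 to 1.09 at week 26. A much steeper assumed hazard, proportional to 1 + a·exp(−t/30) with a = 3 to 9, gives 1.30 to 1.37 and 1.14 to 1.23.

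**Do other planned analyses recover these deaths?**
- The FAS adverse-event analysis ends at the last dose, which a never-dosed patient does not have. If the patient is also coded as not started within the window (OTH13), SAP 2.2 removes them from the FAS.
- The three adverse-event periods in SAP 2.8.1 start at randomisation or later, but they set the time window, not the analysis set. The one-dose requirement stays.
- Disposition (SAP 2.3.1) is in all randomised patients, by epoch and arm, with reason for discontinuation. A pre-dose death would show there if death is a listed reason.

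**The case against.** The strongest replies, and what stands of each:

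- **The plan never says that deaths are counted only in dosed patients.** A reader might infer that it does. SAP 2.8.2 names no set, and its flags follow the word for inclusion, so the list is not closed. This stands as a limit on wording: the restriction comes from the general rule. But both documents state that rule, and nothing visible overrides it for deaths.
- **The deaths are not lost to the report.** This stands in part, because the disposition table may show them. That table is not a death summary, however, and a patient withdrawn undosed could die later without appearing there.
- **Redacted SAP text may hold a death count from randomisation.** This stands. The contents list has blacked-out entries, so one cannot say that no such analysis is planned.
- **A never-dosed patient may stay in the FAS.** TRT04 alone excludes from the SAF only, and a patient who dies before the window closes has not clearly breached it. This is true, and it would put the patient in the FAS repeat of the primary analysis. It does not put the death in the safety summary.
- **The effect is small and safety is descriptive.** This stands. With about 14.9 v 12.7 deaths, SE(log ratio) = √(1/14.9 + 1/12.7 − 2/500) = 0.377, so a ratio of 1.18 has a 95% interval of about 0.56 to 2.46. Mortality is neither a primary nor a secondary endpoint.

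**Conclusion.** The concern holds in a limited form. Under the default rule, the death summary leaves out deaths before the first dose and is expected to leave out more of them in the Post-discharge arm. The expected size is about 3 to 4 Post-discharge deaths and fewer than one Pre-discharge death per 500. That gives an apparent Pre/Post ratio of about 1.16 to 1.19 at week 10 and 1.05 to 1.07 at week 26 when the true ratio is 1.00. This assumes equal true mortality, the protocol's 15 to 20% one-year figure, a constant hazard, and the discharge and dosing patterns above. Trial patients selected by the entry criteria may have lower mortality.

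Two stronger readings are not supported. A reader might take the whole range of 3 to 24 days as the bias, but the Pre-discharge arm has its own period of up to 7 days, and the average difference is about 10 days. A reader might also expect ratios of 1.3 or more at week 10. Those need a steep early hazard that decays over about 30 days, which protocol 1.1 does not give. The direction is an expectation under equal mortality, not a documented result.

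**What to change.** In SAP 2.8.2:

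1. Add a descriptive summary of all deaths from randomisation to week 10, and to week 26 with the extent of known follow-up stated, in all randomised patients by randomised arm.
2. Add a before-first-dose flag to the two existing flags.
3. Give the same as-randomised count for SAEs, without a last-dose cut-off.
4. Keep the SAF table alongside and name its analysis set.

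A Kaplan-Meier estimate is optional; simple counts are enough in a descriptive safety plan.

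The cost is SAP wording and one or two tables. The data largely exist: SAEs are reportable from consent (protocol 7.3.2), and vital status is already sought for patients not followed up for the primary endpoint (protocol 9.4.3). The main weakness is follow-up. Patients who stop the drug in the Treatment Epoch end the study at Visit 199 (protocol 5.5.9), and undosed patients are withdrawn under protocol 3.1. Vital status after week 10 will therefore be incomplete for the first group, and possibly from an earlier point for the second. The number with unknown status in each arm should be reported with the counts.

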## 2.8.3 Laboratory data

Central laboratory data will be summarized by presenting shift tables using extended normal ranges (baseline to most extreme post-baseline value), by presenting summary statistics of absolute data and change from baseline values (mean, medians, standard deviations, ranges) at each visit for which assessments are available for the parameters as in Table 2-4, and by the flagging of notable values in data listings by the criteria defined in Table 2-5. Listings will be provided for local laboratory evaluations for hematology and biochemistry parameters, as available.

Any values below the limit of quantification will be analysed as 0.5\* the lower limit. Any values above the limit of quantification will be analysed as 1.5\*the upper limit.

Liver safety analyses include frequencies of treatment-emergent elevations, a shift table of baseline and worst post-baseline values, respective narrow and broad "Possible drug related hepatic disorders - comprehensive search" SMQ and preferred term frequencies, eDISH plots, and narratives for any patients discontinued due to liver function abnormalities.

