Symptomatic hypotension is more likely to occur if the patient has been volume-depleted, e.g., by diuretic therapy, dietary salt restriction, diarrhea or vomiting. Sodium and/or volume depletion should be corrected before starting treatment with LCZ696, however, such corrective action must be carefully weighed against the risk of volume overload.

When initiating therapy or during dose titration with LCZ696, blood pressure should be monitored at an appropriate interval, in accordance with normal clinical practice.

If hypotension occurs, dose adjustment of diuretics, concomitant antihypertensive drugs, and treatment of other causes of hypotension (e.g. hypovolemia) should be considered. If hypotension persists despite such measures, the dosage of LCZ696 should be reduced or temporarily discontinued. Permanent discontinuation of therapy is usually not required.

Risk of renal impairment

As for any drug that acts on the renin-angiotensin-aldosterone system, use of LCZ696 may be associated with decreased renal function. In PARADIGM-HF, the incidence of clinically relevant renal impairment was low and associated treatment discontinuation was observed less frequently in patients receiving LCZ696 (0.65%) compared to enalapril (1.28%).

There is very limited clinical experience in patients with severe renal impairment (estimated GFR <30 ml/min/1.73 m²), these patients may be at greater risk of hypotension and therefore will be excluded from the study participation. There is no experience in patients with end-

Protocol No. CLCZ696B2401

stage renal disease, LCZ696 is not recommended in these patients and should be permanently discontinued if such condition should develope during the study.

Assessments of patient's renal function will be performed during routine study visits (i.e., serum creatinine and eGFR).

In patients with moderate renal impairment (eGFR 30-60 ml/min/1.73 m²), the starting dose will be 50 mg twice daily. Down titration of LCZ696 should be considered in patients who develop a clinically significant decrease in renal function

Concomitant administration of LCZ696 with ACEI, ARBs or direct renin inhibitor aliskiren is prohibited.

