5.5.7.1 Heart failure medications for chronic therapy and other cardiovascular medications

Patients should be on an optimal medical regimen of HF medications except ACE inhibitors and ARBs during the whole study duration. The use of an MRA and a β-blocker (if tolerated) should be considered in all patients eligible for this study. In self-identified black patients, the use of isosorbide dinitrate/hydralazine hydrochloride (e.g., BiDil®) should be considered. Every effort should be made to keep the dose level of these background HF medications stable throughout the entire study. However, if the patient's condition warrants a change in any of these medications (for example, if the investigator believes a medication is causing an adverse event), it is allowed at the discretion of the study investigator.

Diuretics may be used and may be adjusted throughout the length of the study at the discretion of the investigator.

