Blood hematology	L, S	С								С				С
Blood biochemistry, Local Laboratory	S													
Blood biochemistry Central laboratory		С		С			С			С				С
Serum creatinine, potassium, ALT, AST, total bilirubin - Local Laboratory	Ł	L		L		L	L	L	L	L	L	L	L	L
Serum creatinine, potassium, ALT, AST, total bilirubin - Central laboratory						С		С	С		С	С	С	
Urine dipstick		L				L	L	L	L	L	L	L	L	L
Urine albumin &		С		С		С	С	С	С	С	С	С	С	С

Epoch	Screen- ing				Treatm	nent							Follow-ı	ıp
Visit	1	101 Random -ization	Start date of Pre discharge treatment	102 Discharge	Start date of Post- discharge	103	104	105	106	199 & TD and/or PPW	201	202	203	End of Study Visit 299 & TD and/or PPW
Day	-3-to-1	1				14§	28§							
Weeks AFTER Randomization						2 §	4 §	6§	8§	10§	14 ^Φ	18 ^Φ	22 ^ф	26 ^ф
Weeks of follow-up											4	8	12	16
creatinine- Central laboratory														
Pregnancy test *	Х									Х	Х	Х	Х	Х
Contact IRT	Х	Х		Х		Х	Х	Х	Х	Х	Х	Х	х	Х
Dispense Study Medication / DAR			А		В	X**	X**	X**	X**	X**	X**	X**	X**	
Drug accountability						D	D	D	D	D	D	D	D	D
Adverse events							Х							
Study Completion														X

TD = study discontinuation
PPW = Premature patient withdrawal
X = assessment to be recorded on clinical data base

Epoch	Screen- ing		Treatment									Follow-up			
Visit	1	101 Random -ization	Start date of Pre -discharge treatment	Discharge	Start date of Post- discharge	103	104	105	106	199 & TD and/or PPW	201	202	203	End of Study Visit 299 & TD and/or PPW	
Day	-3-to-1	1				14§	28§								
Weeks AFTER Randomization						2§	4 §	6§	8§	10§	14 ^Φ	18 ^ф	22 ^ф	26 ^ф	
Weeks of follow-up											4	8	12	16	

S = assessment to be recorded on source documentation only

L = assessment carried out through the Local laboratory (and entered manually in the data base)

D = These assessments are source documentation only and will not be entered into the CRF, but collected and transferred to the database

- * Please, see Section 6.5.7 for details.
- ** dispensing study medication depending upon change of dose level, or refilling the same dose
- § Visit should occur within a window of +/- 3 days of the designated calendar day
- ^Ф Visit should occur within a window of +/- 7 days of the designated calendar day
- For patients with 'prolonged hospital stay' (see Section 3.1 Study design) the assessments assigned to the Discharge visit should be carried out BEFORE starting LCZ696 treatment

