6.5.7.3 Urinalysis

First morning void urine samples should be collected from patients for the **dipstick assessment**. Dipstick measurements for specific gravity, pH, protein, glucose, bilirubin, ketones, WBC, and blood will be performed. WBC sediments will also be measured in case of an abnormal dipstick test.

A spot urine sample could be collected for the assessment of albumin and creatinine to be sent to the Central laboratory.

Please, refer to Table 6-2 for the laboratory (central or local) and timing of collection.

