**Table 2-4 List of laboratory tests**

Hematology	Biochemistry	Urine assessments
Hematocrit	Alanine amino-transferase (ALT)	Albumin
Hemoglobin	Albumin	Creatinine
Platelet Count	Alkaline phosphatase	Urine dipstick
Red Blood Cells count	Aspartate amino-transferase (AST)	
WBC Differential	Blood urea nitrogen (BUN) (OR urea ONLY for local laboratory unable to assess BUN)	
White Blood Cells count	Calcium	
	Chloride	
	Creatinine	
	eGFR	
	Fractionated bilirubin (if total bilirubin > 2x ULN)	
	Glucose	
	Lipid profile (total cholesterol, LDL, HDL, and triglycerides)	
	Potassium	
	Sodium	
	Total Bilirubin	
	Total protein	

	Uric Acid	
--	-----------	--

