### 5.3 Laboratory parameters derivations

See section 2.8.3.

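### Spot-urine albumin and creatinine are summarised as separate concentrations with no albumin-to-creatinine ratio, so the descriptive urine albumin tables mix albumin excretion with urine dilution (minor)

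*SAP*

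**What the plan says.** Protocol 6.5.7.3 describes the sample: "A spot urine sample could be collected for the assessment of albumin and creatinine to be sent to the Central laboratory". First-morning urine is specified there for the dipstick, but the quantitative sample is only called a spot sample. Table 6-1 marks central urine albumin and creatinine at Visits 101, 102, 103, 104, 105, 106, 199, 201, 202, 203 and 299, which is every numbered visit except Visit 1.

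The SAP table headed "Table 2-4 List of laboratory tests" has three urine entries: albumin, creatinine and dipstick. For central laboratory data, SAP 2.8.3 plans "shift tables using extended normal ranges (baseline to most extreme post-baseline value") and, in the same sentence, "summary statistics of absolute data and change from baseline values (mean, medians, standard deviations, ranges) at each visit". Values below the quantification limit are set to half the lower limit, and values above it to 1.5 times the upper limit. SAP 5.3, the place for laboratory derivations, says only "See section 2.8.3".

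On diuretics, protocol 5.5.7.1 says: "Diuretics may be used and may be adjusted throughout the length of the study at the discretion of the investigator".

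**The concern.** The concentration of albumin in a spot sample depends on how much albumin is excreted and on how much water it is excreted in. Urine creatinine from the same sample carries the same dilution, so dividing one by the other removes it. The trial collects both, and the readable plan then tabulates them apart. The creatinine table on its own will largely track urine concentration.

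The protocol gives reasons to expect dilution to vary:

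- Baseline (Visit 101) is in hospital, soon after acute treatment, while most later samples are from outpatients.
- Diuretics may change at any time.
- Protocol 1.1 lists natriuresis and diuresis among the possible effects of the study drug's mechanism.

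At stake is whether the urine albumin tables can be read at all. An apparent rise or fall could be a change in urine concentration, or such a change could mask a real one.

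**Working it through.** The plan states no figure for this point, so there is nothing to reproduce. The check is a comparison of the texts, a visit count and two identities.

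**1. Is a ratio derived anywhere readable?** Table 2-4 has no ratio, 2.8.3 defines none, and 5.3 points back to 2.8.3. Table 2-5 (notable values) covers hematology and blood chemistry only. The answer for the readable text is no.

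**2. How much data is involved?** Table 6-1 has 12 numbered visits (1, 101 to 106, 199, 201 to 203, 299). Urine albumin and creatinine are scheduled at 12 − 1 = 11 of them. One is baseline, which leaves up to 10 post-baseline samples per patient.

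**3. Effect of dilution on one sample.** Concentration = excretion / volume. If volume is multiplied by *f* at unchanged excretion, concentration changes by 1/*f* − 1. The ratio changes by 0, because *f* cancels.

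| *f* (assumed) | Raw albumin | Albumin/creatinine ratio |
|---|---|---|
| 1.25 | 1/1.25 − 1 = −20% | 0% |
| 1.5 | 1/1.5 − 1 = −33% | 0% |
| 2 | 1/2 − 1 = −50% | 0% |

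In the other direction, urine 1.3 to 1.5 times more concentrated than at baseline raises raw albumin by 30% to 50%.

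**4. Added noise.** On the log scale, log albumin = log ratio + log urine creatinine. If the two terms on the right are independent, var(log albumin) / var(log ratio) = (s_R² + s_U²) / s_R². None of the SDs below is in the documents.

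- Single values, s_R from 0.8 to 1.5 and s_U from 0.4 to 0.8. Smallest: (1.5² + 0.4²) / 1.5² = 2.41 / 2.25 = 1.07. Largest: (0.8² + 0.8²) / 0.8² = 2.0.
- Changes from baseline, SD of log-ratio change 0.6 and within-patient s_U of 0.3, 0.5 or 0.7 at each of two visits: (0.36 + 2 × s_U²) / 0.36 = 1.50, 2.39 or 3.72.

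The inflation therefore runs from about 1.1 to 3.7, depending on assumptions the documents cannot settle.

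**5. Could dilution differ between arms?** Pre-discharge patients take their first dose at least 12 hours before discharge. Post-discharge patients start between the day after discharge and 14 days after it. At Visit 102 normally only the Pre-discharge arm is on LCZ696. Randomization is at least 48 hours before planned discharge, so a Post-discharge patient may start as late as day 2 + 14 = 16 or beyond, after Visit 103 at day 14. A difference at these early visits is plausible. Its size is unknown.

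**6. Do the shift tables help?** They use the same unnormalised values and take the most extreme of up to 10 post-baseline results, so they tend to pick out samples at the extremes of dilution.

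**The case against.** Several stronger readings are tempting, and the documents do not support them.

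- *The renal safety signal is confounded.* A reader might infer this because renal impairment is a named risk. But protocol 3.6 says assessments of patients' "renal function will be performed during routine study visits (i.e., serum creatinine and eGFR"). The Appendix 5 triggers use serum creatinine and eGFR. The SAP summarises serum creatinine above 265 µmol/L, eGFR falls of 25% and 40%, notable BUN and serum creatinine changes, and events from the renal CRF pages. None of these depends on urine dilution, and the readable text gives urine albumin no threshold or endpoint role.
- *The values are summarised only as means and changes.* Shift tables are planned too, though on the same raw scale.
- *The plan never forms the ratio.* Parts of the SAP are blacked out, and its introduction refers to table shells and data set specifications that are not visible. Absence is shown for the readable text only.
- *The comparison between arms is biased throughout.* Both arms have a pre-drug baseline, both go from hospital to outpatient care, and diuretics may be adjusted in both. Most of any shift is common to the arms. A difference is plausible mainly at the early visits.
- *Apparent doublings of urine albumin will be inflated.* No doubling criterion for urine albumin is planned, and any such percentage would rest on assumed SDs.

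It is also fair to say that the ratio could be computed later from the stored data. All of this narrows the point. It does not make the urine albumin tables interpretable as planned.

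**Conclusion.** The point stands as a minor one. In the readable SAP, the descriptive urine albumin summaries mix excretion with dilution, although the paired measurement that removes dilution is collected at the same visits. Change from baseline within each arm is most exposed. Differences between arms are exposed mainly around Visits 102 and 103. The illustrative figures (20% to 50% lower concentration for 1.25- to 2-fold dilution, variance inflation of about 1.1 to 3.7) rest on assumed dilution factors and SDs and on independence of log ratio and log urine creatinine. They show the mechanism and are not estimates for this trial. Renal safety as assessed through serum creatinine, eGFR, BUN and renal events is untouched, as are the primary and secondary endpoints.

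**What to change.** Add a urine albumin-to-creatinine ratio to SAP Table 2-4, and define it in 5.3 from the paired central results of the same visit, with its unit. State that the quantification-limit rule of 2.8.3 is applied to each component before division. Where albumin has been substituted, the ratio still moves with urine creatinine, so show the number of such values per visit.

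Summarise the ratio by arm and visit as a geometric mean and a geometric mean ratio to baseline. SAP 2.1 already allows geometric means where appropriate. Keep the summaries of the raw concentrations, because protocol 9.5.2 specifies raw values and changes from baseline for laboratory data. Keep the new table descriptive, because the same section rules out formal inference for safety analyses.

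The cost is one derived variable and one extra table. No new data are needed, and no visit, dose or clinical rule changes.
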